Meta-Analysis of N-of-1 Trials: The collection of individual N-of-1 trials can be thought of as a set of studies whose results can be combined as in a meta-analysis. The data can be considered as a multilevel structure in which a set of patients is studied with each patient having a set of measurements. Standard multilevel mixed model methods will be used to estimate the average effect and variance within and across patients. Across patient values estimate the average effect in the population of patients studied, while the within-patient estimates describe an improved estimate of each patient's true effect assuming exchangeability across patients. We will fit these models using a Bayesian multilevel model with non-informative priors in order to obtain posterior distributions of the within and between effect sizes. We will then compare the multilevel patient estimates with those from the patient's data alone in order to determine how much the effects change and how much additional precision these estimates gain.

Analysis of Comparative Effectiveness: The experimental design is a simple two-arm randomized trial comparing N-of-1 vs. symptom surveillance. The primary outcome is the change in the AFEQT scale from baseline to 12 weeks. The mean change in each treatment group will be compared by a t-test. The average frequency and severity of AF episodes per week during the final month of each participant's enrollment will be the secondary

outcomes. Their group means will also be compared with a t-test. We will check for balance in covariates across the randomized groups and will adjust for any imbalances by including those covariates in regression analyses and reporting the adjusted treatment effect as a secondary analysis.

Missing Data: A major purpose of this aim is to determine the feasibility and usability of N-of-1 studies for actual application in clinical practice. Therefore, carefully documenting adherence and completion rates and predictors of each will be an important aspect of this study. Within the HeH study, we have found that >90 % of all AF HeH study participants complete all AF-related surveys, including the AFEQT. The primary analysis will be intent-to-treat which uses all participants as randomized. When no endpoint is available, we will assume no change. Further analyses will employ multiple imputation to fill in missing values, particularly in covariate-adjusted models ([name]-3).

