5.4 Analysis

5.4.1 Comparison of N-of-1 to data tracking

The experimental design for Aim 2 is a two-arm randomized trial comparing N-of-1 vs. symptom surveillance. The primary endpoint is AF severity via the AFEQT from baseline to 10 weeks. Differences between treatment groups will be compared using analysis of covariance with the 10 week measurement as the outcome and the baseline measurement as covariate. We will also test for an interaction between treatment and baseline AFEQT in order to measure possible treatment effect heterogeneity. The average frequency, duration and severity of AF episodes per week during the final month of each patient's enrollment will be secondary outcomes. Their group means will be compared with a t-test. Additional secondary outcomes will include safety events: hospitalizations, emergency room visits, stroke, myocardial infarctions and heart failure. The main analysis will treat each of these as a binary outcome indicating the incidence of any event. We will also investigate models for multiple Version 1.0 5/12/17

events per person if these are common. We will check for balance in covariates across the randomized groups and will adjust for any imbalances by including those covariates in regression analyses and reporting the adjusted treatment effect as a secondary analysis. The null hypothesis of no difference will be tested at a significance level of 0.05.

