5.4.1.2 Missing Data

We will attempt to obtain a 10-week AFEQT value when a patient drops out of the study. When the primary 10-week endpoint is missing for a patient, we will use different approaches to estimate sensitivity of conclusions to the missing data assumption: 1) disregard the missing outcome and discard the patient from analysis; 2) multiple imputation; 3) assume no change from baseline to 10 weeks. The third analysis is likely to be conservative, but makes a fairly strong assumption about the missing not at random assumption (MNAR).

Other endpoints such as average frequency, severity, duration and number of safety events will be calculated based on the data reported. We will assume that days where no safety events or AF events are reported are event-free and so there will be no missing values for the other outcomes.

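### The protocol and the SAP attach different tests and time labels to the primary AFEQT comparison, the SAP ranks no missing-data rule as primary, and neither document says which prevails

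*Protocol*

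**What the plan says.** **Protocol 1.7.2.** The outcome and time point are: "The primary outcome is the change in the AFEQT scale from baseline to 12 weeks". The test follows directly: "The mean change in each treatment group will be compared by a t-test". The Missing Data paragraph adds "The primary analysis will be intent-to-treat which uses all participants as randomized" and "When no endpoint is available, we will assume no change". Multiple imputation is left to further analyses.

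**SAP 5.4.1.** "The primary endpoint is AF severity via the AFEQT from baseline to 10 weeks". The arms are compared by "analysis of covariance with the 10 week measurement as the outcome and the baseline measurement as covariate", and "The null hypothesis of no difference will be tested at a significance level of 0.05". The section names no analysis set.

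**SAP 5.4.1.2.** If the 10-week value is missing, "we will use different approaches to estimate sensitivity of conclusions to the missing data assumption". Three approaches follow: drop the patient, impute multiply, or assume no change. None is called primary.

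**When the AFEQT is collected.** Protocol 1.4.1 and 1.5 put the follow-up survey at the end of the 10-week programme: 6 weeks of testing plus 4 of lifestyle change in the N-of-1 arm, 10 weeks of tracking in the other. SAP Table 2 (section 4.1) lists baseline and 10 weeks. SAP 4.2 also ends at 10 weeks, but says the survey is given monthly and equates baseline with randomization. Under Protocol 1.5 and SAP 5.3, randomization happens at consent. The baseline AFEQT comes later, after about two weeks of device shipping and the device set-up.

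**The concern.** This is the main between-arm comparison of the trial. A reader who follows the protocol and one who follows the SAP would run different tests on the same data and could report different verdicts at the 0.05 level. Neither document cites the other as governing. The SAP is marked Version 1.0 of 5/12/17, and the protocol text carries no version date, so even the order in time cannot be read off.

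Whether the missing-data rule is settled depends on which document is used. Unlike the choice of test, that rule can change the estimate itself.

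The 12-week label matches no AFEQT survey in the protocol's own schedule.

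**Working it through.** **Inputs.** 239 per arm, a 5-point difference, SD 19 and 80% power (Protocol 1.7.1, SAP 5.2); alpha 0.05 (SAP 5.4.1), taken as two-sided. The documents give neither the SD of the change nor the correlation ρ between baseline and follow-up AFEQT. I assume SD 19 at both visits and ρ = 0.3, 0.5 and 0.7.

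**The plan's own figure.** A two-sample comparison with SD 19 needs 2 × [19 × (1.960 + 0.842) / 5]² ≈ 227 per arm. At 239 per arm the power is 81.9% (noncentral t), in line with the stated 80%.

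**Test against test.**
- SD of the change: 19 × √(2(1 − ρ)).
- ANCOVA residual SD: 19 × √(1 − ρ²).
- Standard error of the difference: SD × √(2/239).
- Correlation between the two test statistics: √((1 + ρ)/2). The probability of opposite verdicts then comes from the bivariate normal distribution with a true difference of 5.

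| ρ | SD of change | ANCOVA SD | Power, t-test | Power, ANCOVA | Correlation of tests | Opposite verdicts |
|---|---|---|---|---|---|---|
| 0.3 | 22.48 | 18.12 | 68% | 85% | 0.806 | 21% |
| 0.5 | 19.00 | 16.45 | 82% | 91% | 0.866 | 12% |
| 0.7 | 14.72 | 13.57 | 96% | 98% | 0.922 | 3% |

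The t-test on change reaches 80% only once ρ is about 0.475 or more. The stated SD of 19 is the SD of the change only at ρ = 0.5.

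**Missing-data rule.** If a fraction m is missing in both arms, unrelated to outcome, setting those changes to zero multiplies each arm's mean change by (1 − m). A 5-point difference becomes 5 × (1 − m):
- m = 5%: 4.75
- m = 10%: 4.5
- m = 20%: 4.0

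These rates are illustrative.

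**Which element drives the verdict.** In simulation at 10% missing (239 randomized per arm, 6,000 runs per setting), with no change assumed under both tests, verdicts differ in 21%, 13% and 3% of trials. With complete data the figures are 21%, 12% and 3%. ANCOVA power under no change versus dropping the patient is 79% vs 81%, 87% vs 88% and 97% vs 97%. Nearly all the disagreement comes from the test.

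**Participants with no baseline.** Someone randomized at consent who never completes the baseline AFEQT has no ANCOVA covariate. The no-change rule gives that person no 10-week score either, because there is nothing to carry forward. A change score could be set to zero; an ANCOVA cannot be run for that person without a further rule.

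**The case against.** The strongest reply is that the documents can be read together: the protocol sets the no-change rule and the SAP adds sensitivity checks that include it. For missing data this largely stands. A reader might infer that the two documents contradict each other there, but the SAP leaves a gap in ranking. What remains is that dropping patients departs from the protocol's all-randomized rule, and the SAP does not repeat that rule.

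It can also be said that, with complete data under randomization, both tests target the same mean difference. That is correct. The conflict in tests affects precision and the p-value, and at a correlation of 0.7 it matters little. It does not follow that either test may be left open.

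A reader might go further and infer an inflated type I error. If either test could be reported after seeing both, the false-positive rate would be 7.8%, 7.3% and 6.8% at the three correlations. That is a worst case, and nothing in the documents suggests such a choice is intended.

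A reader might infer from the 12-week label that a second, later AFEQT exists. The protocol schedules none, but the monthly wording in SAP 4.2 stops one from ruling it out. Counting 12 weeks from randomization, with two weeks for shipping, would fit 10 weeks of programme, but no text makes that link.

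Nor is the recruitment margin (600 started for 478 completers, about 20%) a ceiling on missing AFEQT scores. It is an enrolment allowance for a six-month study. The completion rate above 90% in Protocol 1.7.2 comes from the Health eHeart Study.

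Finally, the documents require only that the tests agree, and the choice belongs to the sponsor. ANCOVA is the natural one because the SAP already plans it and the baseline is already collected.

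**Conclusion.** The concern holds. The primary test and time label conflict, the SAP ranks no missing-data method as primary and states no analysis set, and no text sets precedence. If the SAP were taken to govern, the headline estimate would still be undefined whenever a 10-week AFEQT is missing.

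The choice of test moves power by about 17, 9 and 2 percentage points at correlations of 0.3, 0.5 and 0.7. This rests on an unstated correlation, equal SDs of 19 at both visits and a true 5-point effect. The missing-data rule chiefly affects the estimate, by the proportion missing when missingness is equal in the arms and unrelated to outcome.

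A reader might take SAP 5.4.1 to plan an ANCOVA in all randomized participants. It plans the ANCOVA and the 10-week measurement; the all-randomized set comes from the protocol alone.

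**What to change.** Before unblinding:

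1. In Protocol 1.7.2, replace the 12-week label and the t-test for the primary outcome with the AFEQT at the end of the 10-week programme, counted from the baseline AFEQT, analysed by ANCOVA on baseline as SAP 5.4.1 already plans.
2. State the protocol's all-randomized analysis set in the SAP.
3. Name the same single primary missing-data method in Protocol 1.7.2 and SAP 5.4.1.2, at the sponsor's choice, with the others as sensitivity analyses.
4. Add a rule for randomized participants with no baseline AFEQT, for example multiple imputation of both scores.
5. In SAP 4.2, reconcile baseline as randomization with Protocol 1.5, and the monthly survey with Table 2. Settle whether any AFEQT near 12 weeks exists.

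The cost is wording changes and minor analysis work, with no new data and no extra participants. The DSMB charter (section 2.0) keeps investigators blinded to between-arm results, so the change can be made cleanly while that blind holds.

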Heterogeneity of Treatment Effects (Std HT-1 through 4): HTE between individuals with AF is a major issue that is of particular interest to patients. In secondary analyses, we will test for interactions between treatment and covariates that describe potential pre-specified HTE hypotheses. Predetermined interaction analyses will include testing for effect modification by "lone" AF (age <65 years of age without any cardiovascular risk factor) vs. not, sex, and race (non-Hispanic white race vs. not). Additional post hoc interaction analyses examining currently unrecognized moderators will be planned based on input from patients over the course of the study. These are likely to include testing for effect modification by particular triggers (e.g., setting an early bedtime works well whereas avoiding morning endurance exercise does not). Statistical significance for interaction analyses will use a p-value cut off of \leq 0.01.

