5.4.1.1 Heterogeneity of treatment effects (HTE)

N-of-1 trials may be more effective for some types of patients than for others. In addition, to checking interaction with baseline AFEQT, we will examine interactions of treatment with the potential between-patient modifiers listed in Table 2 in regression models as exploratory analyses. These will include medical history, demographics, medications, mood and sleep.

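### Mood and sleep are recorded only after the arm is disclosed and should not modify or adjust the arm comparison; separately, the SAP omits the protocol's three named interactions and its p ≤ 0.01 cut-off

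*Protocol*

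**What the plan says.** **Protocol 1.7.2 (Heterogeneity of Treatment Effects).** "Predetermined interaction analyses will include testing for effect modification by" three factors: lone AF (under 65 with no cardiovascular risk factor) versus not, sex, and race (non-Hispanic white versus not). It then leaves room for more: "Additional post hoc interaction analyses examining currently unrecognized moderators will be planned based on input from patients over the course of the study". It closes with a threshold: "Statistical significance for interaction analyses will use a p-value cut off of" ≤ 0.01. The whole set is placed among the secondary analyses.

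**SAP 5.4.1.1 (the arm comparison).** "we will examine interactions of treatment with the potential between-patient modifiers listed in Table 2 in regression models as exploratory analyses". Then: "These will include medical history, demographics, medications, mood and sleep". It names no predetermined subset and gives no interaction threshold.

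**SAP 5.4.1.** A treatment-by-baseline-AFEQT interaction will be tested; it is not called exploratory. The section ends: "The null hypothesis of no difference will be tested at a significance level of 0.05".

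**SAP 4.5.** Mood, sleep and stress are assessed daily. Their relationships with treatment and with outcome will be examined, and results will be adjusted for them if those relationships are statistically significant. This applies to the arm comparison as well as to the N-of-1 experiments.

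**Timing.** Table 2 lists every modifier as baseline only, except sleep and mood, which are daily. Under Protocol 1.5, demographics, history, medications and the first AFEQT are collected before the app shows the participant the assigned arm; study activities start after that.

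**The concern.** There are two separate problems.

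The first is validity. A modifier of a randomised comparison should be fixed before treatment can act on it. Mood and sleep are observed only once participants know their arm. The intervention can change sleep directly, because sleep, alcohol and caffeine are themselves triggers on the menu (SAP 5.1). An interaction with such a variable may reflect what the intervention did to sleep, and need not identify patients for whom the intervention works better. The SAP 4.5 rule has a related fault. An association between arm and a variable measured after disclosure may be an effect of treatment, so the rule can call for adjustment exactly when adjustment would remove part of the effect being estimated.

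The second is a mismatch. An analyst working from the SAP alone could not tell which subgroup hypotheses the protocol fixed in advance, how lone AF is defined, or what cut-off applies. The protocol says that heterogeneity is of particular interest to patients, so these results will be read.

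**Working it through.** **1. Are mood and sleep post-disclosure variables?** Table 2 gives 22 modifiers collected at baseline only and 2 (sleep, mood) collected daily. No baseline mood or sleep item appears in Table 2 or in the baseline collection of Protocol 1.5. Stress has no row of its own and appears only as a mood category. Randomisation is generated at consent, but the baseline items and first AFEQT precede disclosure of the arm, so knowledge of the arm cannot have affected them. Daily mood and sleep come later and lack that protection.

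**2. Can an interaction appear when treatment affects nobody's outcome?** This is an algebraic illustration, not trial data. Let U be a patient trait (centred) and let the outcome be Y = βU in both arms. With tracking, sleep is S = U. With N-of-1, the intervention compresses or widens sleep differences, so S = λU with λ ≠ 1.
- Slope of Y on S, tracking: β
- Slope of Y on S, N-of-1: β/λ
- Apparent interaction: β/λ − β = β(1 − λ)/λ, which is not zero although treatment changes no outcome.

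**3. What does adjustment remove?** Let Y = τA + γS + error and S = δA + error, where A is the arm. The total effect of A is τ + γδ. Adjusting for S leaves τ, so γδ is lost. The documents give no values for γ or δ, so the size cannot be stated.

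**4. Are the protocol's three interactions in the SAP?**
- Sex and race: rows in Table 2, without predetermined status.
- Lone AF: not a row. The nearest item, in SAP 4.5, is a history of having no disease apart from AF. It has no age limit, so it is a different definition.
- p ≤ 0.01: absent.

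**5. Multiplicity.** The documents give no false-positive rate for interactions, so there is no plan figure to reproduce. Inputs: 22 + 2 = 24 Table 2 modifiers, plus baseline AFEQT = 25, with one test per modifier and no true interaction. Under independence, P(at least one false positive) = 1 − (1 − α)^k.

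| Tests | α = 0.05 | α = 0.01 |
|---|---|---|
| 3 (protocol's named set) | 1 − 0.95³ = 14.3% | 1 − 0.99³ = 3.0% |
| 23 (baseline modifiers + AFEQT) | 69.3% | 20.6% |
| 24 (Table 2) | 70.8% | 21.4% |
| 25 (Table 2 + AFEQT) | 72.3% | 22.2% |

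Independence is generous to these figures, because Table 2 contains related pairs (sex and gender identity, coronary disease and heart attack, education and income). Simulating equally correlated normal test statistics for 24 tests (200,000 draws; the correlations are assumptions) gives:

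| Correlation | α = 0.05 | α = 0.01 |
|---|---|---|
| 0.1 | 69% | 21% |
| 0.3 | 59% | 18% |
| 0.5 | 46% | 13% |
| 0.7 | 31% | 9% |

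The 23-test row shows that removing mood and sleep barely changes multiplicity. The reason to remove them is validity.

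**The case against.** The SAP already labels every Table 2 interaction exploratory, and exploratory work may range widely. The 0.05 level closes the section on the arm comparison and is not attached to interactions, and silence in the SAP does not cancel the protocol's 0.01. Nor is the protocol's plan a closed set of three: it adds an open-ended group of post hoc interactions, and its 0.01 covers those too. Sex and race remain examinable, as do the age and history items from which a lone AF variable could be built. Neither document states which takes precedence, so it cannot be shown that the SAP removed anything.

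All of this stands, and it rules out several stronger readings. A reader might infer that the SAP replaced 0.01 with 0.05 for interactions; it gives them no threshold. A reader might set 72% against 3%; that compares the SAP's whole list with only the named part of the protocol's plan. A reader might take 0.01 as the protocol's line between confirmatory and exploratory claims; the protocol applies it to interaction analyses generally and calls none of them confirmatory.

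What the objection does not answer is the use of mood and sleep. Calling an analysis exploratory lowers the weight of its result, but it does not make a variable that treatment can change into a valid modifier. Nor does the label cover the adjustment rule in SAP 4.5.

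**Conclusion.** The point holds in two parts. The firmer part is that mood and sleep, and stress in SAP 4.5, should not serve as modifiers of, or covariates in, the arm comparison. This rests on the documents' own timing and on the intervention being able to change these variables; it needs no multiplicity argument, and its size cannot be computed from the documents. The second part is a real mismatch: the three named interactions, the lone AF definition and the 0.01 cut-off are missing from the SAP, and the status of the baseline AFEQT interaction is unstated.

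A reader might conclude that a false subgroup finding is likely. The documents do not support that without conditions. The 72% requires 0.05 on each of 25 independent tests. For 24 tests it falls to about 31% to 59% at assumed correlations of 0.7 to 0.3, and at 0.01 the 25-test figure is at most about 22%. A reader might also infer that the primary analysis is compromised. SAP 5.4.1 specifies that model with baseline AFEQT as its covariate, while SAP 4.5 does not say which results would be adjusted, so that sentence needs clarifying. This is a minor point on the secondary and exploratory analyses.

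**What to change.** In the SAP:
- **4.5 and 5.4.1.1:** for the arm comparison, restrict modifiers and adjustment covariates to variables measured at baseline. Remove daily mood, sleep and stress, and remove the rule that adjusts for them when relationships are significant.
- **5.4.1.1:** list lone AF (with the protocol's definition and the risk factors that count), sex, and race (non-Hispanic white versus not) as the predetermined interactions, with p ≤ 0.01.
- **5.4.1:** state whether the baseline AFEQT interaction is predetermined or exploratory, and which cut-off applies.
- Keep the remaining Table 2 interactions exploratory, as they are already labelled.

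The three named tests at 0.01 carry a 3.0% chance of any false positive under independence, or 1 − 0.99⁴ = 3.9% if baseline AFEQT joins them.

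The cost is wording only: no new data, no change in sample size and no added burden. The downside is fewer nominally significant subgroup results. Because patients suggested mood and sleep (SAP 4.5), they can still be described by arm as variables that treatment may affect.

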1.8 Safety and Adverse Events (AE)

1.8.1 Adverse Event Reporting

Participants will receive monthly prompts via the application about the following things: hospitalizations (AF, emergency department, cerebrovascular event, myocardial infarction or heart failure), antiarrhythmic medication changes and ablation plans.

We will share reports with the DSMB outlining the results of the above survey.

